3.2 Recruitment Targets

Up to 1200 participants will be recruited from the 8 different disease cohorts. The numbers recruited per cohort will vary as indicated below.

Initiation of recruitment into each cohort will be staggered with lymphoid malignancy, immune-mediated rheumatic diseases, end stage kidney, chronic liver disease, and gastrointestinal disease on immunosuppressive therapy and patients being prioritised in the initial recruitment phase of the trial.

The target recruitment for the study components (see Section 12.2.6 for power calculations) are:

- Main study - minimum of 1100 participants will contribute to the analysis
- Randomised sub-study – minimum of 300 participants will contribute to the analysis

3.2.1 Anticipated Recruitment by Disease Cohort

3.2.1.1 Solid Cancer

Target 80 participants

3.2.1.2 Lymphoid Malignancies

Target 320 participants. Target recruitment per disease cohort sub-type:

- Aggressive B-Non Hodgkin Lymphoma (NHL) - 40 participants
- Chronic lymphocytic leukaemia (CLL) - 80 participants
- Hodgkin Lymphoma - 40 participants
- Indolent B NHL (except CLL and small lymphocytic lymphoma (SLL)) - 80 participants
- Myeloma - 80 participants

3.2.1.3 Immune-mediated Rheumatic Diseases

Target 160 participants.

3.2.1.4 End Stage Kidney Disease

Target 160 participants.

3.2.1.5 Chronic Liver Disease

Target 80 participants.

3.2.1.6 Gastrointestinal Disease on Immune Suppressive Therapy

Target 80 participants.

3.2.1.7 Haematopoietic Stem Cell Transplant

Target 80 participants.

3.2.1.8 Primary Immunodeficiency

Target 160 participants.

3.2.1.9 CAR-T Cell Therapy

Target 80 participants.

4 ELIGIBILITY

The eligibility criteria for OCTAVE-DUO aim to allow inclusion of patients with a range of conditions that impact on their immune status. The study aims to reflect the patient population who may be eligible for a third dose of vaccine in the future and therefore the study exclusion criteria are limited to those that would preclude administration of SARS-CoV-2 vaccines in the normal population, in accordance with the vaccines' applicable product information (see Section 7.1).

Patients meeting the criteria below are eligible to participate in the trial.

4.1 Inclusion Criteria

1. Aged ≥ 18 years.
2. Have an inadequate response to two doses of SARS-CoV-2 vaccine measured at least 14 days after receipt of the second vaccine, defined by SARS-CoV-2 spike antibody response.

An inadequate response is defined as:

- i) **Antibody non-response:** SARS-CoV-2 anti-spike antibodies below the level of detection using the PHE Roche platform [or equivalent assay, see Appendix 1] <0.8 Arbitrary Units (AU)/ml; or
- ii) **Antibody low-response[†]:** SARS-CoV-2 anti-spike antibodies ≥ 0.8 and <400 AU/mL using the Roche platform [or equivalent assay, see Appendix 1]).

[†] *There is no agreed international/WHO cut off for titres of AU following vaccination and serologic assessment. As such, the low responder status for OCTAVE-DUO eligibility is by definition arbitrary. We have examined the serology levels obtained in the OCTAVE study, compared with PITCH (health care workers without vulnerable conditions) and elected to choose a titre that equates to approximately 30% of the OCTAVE population – this equates to approx. 400 AU hence this selection for this part of the eligibility criteria. Since in practice all vulnerable groups will receive a re-boost in due course, by choosing the lowest tertile for evaluation of enhancement of response, we are maximising the pragmatic value of the study in terms of policy advice, and determination of magnitude of immune response, representing our primary outcome. Moreover, we are thereby ensuring rapid and representative recruitment from the variety of vulnerable patient groups in the study protocol.*

- 3. Anticipated life expectancy of 6 months or greater.
- 4. Fall into one (or more) of the following patient cohorts who will meet disease relevant classification, disease state, and staging according to established international standards:
 - o **Diagnosed with any of the following solid cancers:**
 - Breast
 - Lung
 - o **Diagnosed with any of the following lymphoid malignancy categories:**
 - Aggressive B-NHL
 - CLL
 - Hodgkin Lymphoma
 - Indolent B NHL (except CLL and SLL)
 - Myeloma
 - o **Diagnosed with the following rheumatic/inflammatory conditions:**
 - Rheumatoid Arthritis
 - Psoriatic Arthritis
 - Seronegative Arthritis
 - Spondyloarthritis
 - Anti-neutrophil cytoplasm antibodies (ANCA) -associated Vasculitis
 - Systemic Lupus Erythematosus (SLE)
 - Psoriasis

- Crohn's disease / Ulcerative colitis
 - Autoimmune hepatitis
 - o **Diagnosed with the following chronic renal conditions:**
 - End stage kidney disease secondary to any cause
 - Renal transplant following end stage kidney disease
 - o **Diagnosed with the following chronic liver conditions:**
 - Liver cirrhosis
 - Liver transplantation
 - Chronic liver disease (of any stage) on immune suppressive therapy
 - o Diagnosed with gastrointestinal disease and on immune suppressive therapy
 - o **Diagnosed with primary antibody deficiency:**
 - Defined as any patient who is on immunoglobulin replacement therapy or any patient with an IgG <4g/l and on prophylactic antibiotics.
 - o **Haematopoietic stem cell transplant[†]:**
 - Previously treated with autologous or allogeneic haematopoietic stem cell transplant for any indication and with any conditioning regimens and intensities, who have not relapsed post-transplant
 - o **CAR-T Cell therapy[†]:**
 - Previously treated with CAR-T cell therapies for any indication, irrespective of remission status
5. Participant is willing and able to comply with trial requirements.
6. For the randomised sub-study only, female participants of childbearing potential* must be willing to ensure that they or their partner use acceptable effective contraceptive methods until 3 months after the re-boost immunisation. See Section 7.4 and definition of acceptable effective contraceptive methods.

** Defined as a fertile woman, following menarche and until becoming post-menopausal unless permanently sterile. Permanent sterilisation methods include hysterectomy, bilateral salpingectomy and bilateral oophorectomy. Postmenopausal is defined as no menses for 12 months without an alternative medical cause.*

[†] Note: HSCT and CAR-T recipients who have received any SARS-CoV-2 vaccine pre-procedure and are receiving a re-vaccination course post HSCT/CAR-T are eligible for recruitment

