	
• For the randomised sub-study only, patients who are pregnant or lactating at trial entry or planning to become pregnant within 3 months after re-vaccination.
Blood Sample Collection	Whole blood, serum, plasma, and where possible peripheral blood mononuclear cells (PBMC) will be collected at the following time points: 
• Pre-re-boost vaccine (baseline)• 21 (+14) days post-booster
Trial Duration	Patients are expected to be recruited over 3 months and followed up for 3 months in accordance with standard clinical practice for the relevant disease cohort.
Contacts	
Sponsor: University of Birmingham
 
Chief Investigator: [name], University of Glasgow
 
OCTAVE-DUO Trial Office: Cancer Research UK Clinical Trials Unit (CRCTU), University of Birmingham, [name] ✉ [contact]

SCHEDULE OF EVENTS

	Screening	Trial Entry	Baseline Prior to re- vaccination	Re-vaccination¹	Post-re- vaccination² 21 days post re- vaccination	3-month follow- up Seen in accordance with clinical practice³
Eligibility assessment (including dip stick pregnancy test)	x					
Consent	x					
Measurement of SARS-CoV-2 spike antibody response	(x) ⁴					
Randomisation		x				
Re-vaccination				x		
Data collection		x	x		x	x
Assessment of adverse events					x	
Research blood samples ⁵			X ⁶		x	
Participant Diary Booklet ⁷			x		x	

Key

¹ At least 14 days after receipt of the second dose of vaccine

² Minimum 21 days + 14 days post re-boost vaccination

³ Three months after re-vaccination, where possible data collected retrospectively from participants medical records, telephone follow-up permissible

⁴ For the solid cancer, haematopoietic stem cell transplant and CAR-T cell therapy disease cohorts only: where a result is not available from a previous study or antibodies levels are not available from disease site specific clinics, SARS-CoV-2 spike antibody response can be measured as a screening assessment using one of the assays listed in Appendix 1

⁵ Research blood samples include: Whole blood, serum, plasma, and where possible peripheral blood mononuclear cells (PBMC)

⁶ Research blood sample to be collected -14 to 0 days before re-boost vaccination

⁷ Participant Diary Booklet handed out at baseline and collected at post re-vaccination appointment to aid in collection of Adverse Event (AE) data

[figure not shown]

TRIAL DESIGN

[figure not shown]
[figure not shown]

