4.2 Exclusion Criteria

1. Receipt of any vaccine within 30 days before trial entry, with the exception of: a SARS-CoV-2 vaccine which is allowed ≥ 14 days prior; or a flu vaccination which is allowed ≥ 7 days prior.
2. For aggressive B-NHL or Hodgkin lymphoma only, participants on active systemic treatment or within 4 weeks of completion of systemic treatment.
3. Any known contraindications as specified in the applicable product information (see Section 7.1) including but not limited to:
 - o Known allergy or hypersensitivity to any of the trial IMPs or any of the trial drug excipients; and
 - o History of anaphylaxis to prior COVID-19 vaccinations, or any component of the vaccine.
4. In the judgement of the Investigator, the patient is unsuitable to participate in the trial or is unlikely to comply with trial procedures.
5. For the randomised sub-study only, patients who are pregnant or lactating at trial entry or planning to become pregnant within 3 months after re-vaccination.

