7.2 Administration of Investigational Medicinal Products

Participants should receive their re-boost vaccine a minimum of 14 days after their second booster.

The administration of the Pfizer and Moderna SARS-CoV-2 vaccines should be postponed in individuals suffering from acute severe febrile illness. The presence of a minor infection and/or low-grade fever should not delay vaccination.

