7.3.4 Post Re-boost vaccination

Participants will be required to attend clinic for the collection of the post re-boost vaccination research blood sample which must be collected on day 21 (as a minimum) or within an additional 14 days (by day 35). See Section 7.5 for details of research blood sample collection.

Participant Diaries should be collected from the participant and used as a guide to complete the Adverse Event Form.

The following forms should be completed at this time point:

- Adverse Event Form
- Research Blood Sample Collection Form

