12.2.1 Primary Outcome Measures

The primary outcome assessment will be based on the immune response observed in the total combined participants recruited to both the Pfizer and Moderna vaccine arms (n=1160). Analysis will be based on the difference in immune response measured using the specified assays at baseline (pre-third vaccination booster) and then at Day 21 post-third vaccination booster using a paired T-Test analysis method.

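### Dose-two failure, entry, baseline and re-boost are all allowed from day 14 after dose two, but the re-boost is not read before day 21, so in recently vaccinated patients the uncontrolled before/after test can count a continuing dose-two rise as re-boost effect

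*Protocol*

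**What the plan says.** Five timing rules in the protocol bear on this point.

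- **Qualifying test** (Section 4.1, criterion 2): the inadequate response is "measured at least 14 days after receipt of the second vaccine, defined by SARS-CoV-2 spike antibody response". One result suffices. The text explains the 400 AU/mL cut-off at length but gives no reason for 14 days.
- **Trial entry** (Section 4.2, criterion 1): recent vaccines are excluded, except "a SARS-CoV-2 vaccine which is allowed ≥ 14 days prior".
- **Re-boost**: key note 1 of the Schedule of Events says "At least 14 days after receipt of the second dose of vaccine". Section 7.2 says "Participants should receive their re-boost vaccine a minimum of 14 days after their second booster". The two texts name a different starting dose.
- **Baseline** (key note 6; also Sections 7.3.2 and 7.5.1): "Research blood sample to be collected -14 to 0 days before re-boost vaccination".
- **Post re-boost sample** (Section 7.3.4): it "must be collected on day 21 (as a minimum) or within an additional 14 days (by day 35", counted from the re-boost.

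Section 12.2.1 bases the primary analysis on the "total combined participants recruited to both the Pfizer and Moderna vaccine arms (n=1160" and compares baseline with day 21 by a paired t-test. Sections 3.1, 6.1.1 and 6.1.2 give every randomised patient a re-boost.

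**The concern.** The trial uses two standards for when the antibody response to a dose can be read: 14 days for the dose that is said to have failed, and at least 21 days for the dose under test. Two consequences follow, and they rest on different samples.

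1. **Credit to the re-boost.** This depends on the research baseline. If antibody is still rising from dose two when that sample is taken, the rest of the rise falls inside the before/after difference. Without an un-boosted arm, nothing separates it from the effect of the re-boost.
2. **Misclassification.** This depends on the qualifying test. A patient tested on days 14 to 20 may be labelled a non-responder or low-responder when dose two had not finished acting. Section 4.1 does not require status to be confirmed on the baseline sample. The label is a minimisation factor (Sections 6.1.1 and 6.1.2). It also bears on the first hypothesis in Section 1.1.1, that patients without detectable antibody failed to prime and will not respond to another dose. A slow seroconverter labelled as a non-responder would count wrongly against that hypothesis.

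The randomised comparisons between vaccines should be affected equally in expectation. The exposed results are the pooled primary test and analyses by responder status.

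**Working it through.** **The plan's own figure.** Section 12.2.6.1 states that 1100 pairs give 90% power at an effect size of 0.0978 with alpha 5%, and that 800 pairs give 79% power at the same effect. For a two-sided paired t-test, power comes from the noncentral t distribution with n − 1 degrees of freedom and noncentrality d√n.

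- n = 1100, d = 0.0978: power 89.99%.
- n = 800, d = 0.0978: power 78.9%.

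Both figures reproduce, so the effect size is in units of the SD of the paired differences.

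**Timing, in days after dose two, for the earliest permitted patient.**

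- Entry and baseline: day 14.
- Re-boost: day 14 if given on the same day, or up to day 14 + 14 = 28 if baseline was taken at the front of its window.
- Post sample after a same-day re-boost: 14 + 21 = day 35 to 14 + 35 = day 49.
- Latest post sample: 28 + 35 = day 63.
- Gap between the paired samples: 35 − 14 = 21 to 63 − 14 = 49 days.

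Any dose-two rise in that gap is counted as re-boost response.

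**Sensitivity to drift.** Suppose a share p of pairs would have risen by a further d SD from dose two alone. The spurious mean shift is p × d. Both inputs are assumptions; the protocol supplies neither. The last two columns give the probability that the primary test is significant if the re-boost did nothing (5% with no drift).

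| p | d (SD) | p × d (SD) | n = 1100 | n = 800 |
|---|---|---|---|---|
| 2% | 0.5 | 0.010 | 6.3% | 5.9% |
| 2% | 1.0 | 0.020 | 10.2% | 8.7% |
| 5% | 0.5 | 0.025 | 13.2% | 10.9% |
| 5% | 1.0 | 0.050 | 38.1% | 29.2% |
| 10% | 0.5 | 0.050 | 38.1% | 29.2% |
| 10% | 1.0 | 0.100 | 91.2% | 80.6% |

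The test responds to small shifts because it is large: an observed mean difference of 0.059 SD (n = 1100) or 0.069 SD (n = 800) already reaches p < 0.05.

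**Who could be exposed.** Section 4.1 expressly admits HSCT and CAR-T recipients on a re-vaccination course after their procedure. Those cohorts target 80 + 80 = 160 patients, or 160/1160 = 13.8% of the primary population. That is a ceiling for this group, since only those on such a course with a recent second dose are exposed. The 10% rows need 0.10 × 1100 = 110 pairs. If all came from these cohorts, that would be 110/160 = 69% of them, so the 10% rows are towards the high end.

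**The case against.** The strongest reply is that the day-14 patient is an edge case.

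- Change is measured from a separate research baseline, not from the qualifying result. A late dose-two rise that is complete by baseline is not credited to the re-boost.
- Most patients are found through earlier studies or existing clinic results (Section 5.1), and Section 8.2 describes antibody levels in most cohorts as already assessed outside the study.
- Where the trial orders the test itself, consent and confirmed eligibility come before randomisation, so a baseline on day 14 exactly would need a same-day result.
- Section 12.2 leaves analysis detail to the SAP, where a sensitivity analysis could sit.

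All of this stands, and it limits the point to a minority of unknown size. It does not remove the point: the windows permit the case, and the timing rules and the uncontrolled primary test are fixed in the protocol.

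A reader might go further in four ways that the document does not support.

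- **That the bias always favours the re-boost.** The protocol contains no kinetics. Natural change between the samples could be up, flat or down, depending on time since dose two. The bias favours the re-boost only in patients still rising at baseline.
- **That all 160 HSCT and CAR-T patients are affected.** Only an unstated subset is.
- **That drift could account for the whole result.** The figure of 0.0978 SD is what the test can detect with 90% power, not the expected response, so a ratio to it says nothing about what share of the observed rise is spurious.
- **That eligibility should simply start at day 21.** Eligibility precedes randomisation, so a later qualifying test would in practice move the re-boost, which is a clinical rule. It would also still admit patients who rise after day 21.

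**Conclusion.** The point holds in limited form. The protocol reads dose two up to seven days earlier than the minimum it sets for the re-boost (14 against 21), gives no reason, and then relies on a before/after test that cannot tell a continuing dose-two rise from a re-boost response. Patients with an early qualifying test can also be misclassified by responder status, whatever the date of their baseline.

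The size cannot be established from the protocol. With the assumed 10% of pairs and 0.5 SD, the shift is 0.05 SD; with 2% and 0.5 SD it is 0.01 SD. It may be negligible if dose two was usually months earlier. This is a minor, inexpensive improvement and does not threaten the randomised comparisons.

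**What to change.** **Record.** Capture three dates for every patient: second dose, qualifying antibody test, and baseline research sample. Sites need the first two anyway to verify criterion 2. Section 7.3.2 mentions vaccination history, but neither the randomisation items in Section 6.1 nor the form summaries in Table 2 name the dose-two or qualifying-test date.

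**Analyse.** Repeat the primary paired analysis on pairs whose baseline was at least 21 days after dose two, the trial's own reading point, and report the pairs at 14 to 20 days separately. This reduces the bias but does not exclude a rise that continues after day 21. In analyses by non-responder or low-responder status, flag patients whose status rests on a test before day 21.

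**Reconcile.** The sponsor should bring together the intervals in Section 4.1, Section 4.2, Section 7.2, Section 7.3.4 and the Schedule of Events, and settle whether the interval starts at the second dose or, as Section 7.2 puts it, the second booster. No interval for giving vaccine is proposed here.

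**Cost.** Up to three date fields, one additional analysis and one flag, with a loss of pairs in the restricted analysis that should be small. The primary analysis set itself stays as planned.

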4.2 Exclusion Criteria

1. Receipt of any vaccine within 30 days before trial entry, with the exception of: a SARS-CoV-2 vaccine which is allowed ≥ 14 days prior; or a flu vaccination which is allowed ≥ 7 days prior.
2. For aggressive B-NHL or Hodgkin lymphoma only, participants on active systemic treatment or within 4 weeks of completion of systemic treatment.
3. Any known contraindications as specified in the applicable product information (see Section 7.1) including but not limited to:
 - o Known allergy or hypersensitivity to any of the trial IMPs or any of the trial drug excipients; and
 - o History of anaphylaxis to prior COVID-19 vaccinations, or any component of the vaccine.
4. In the judgement of the Investigator, the patient is unsuitable to participate in the trial or is unlikely to comply with trial procedures.
5. For the randomised sub-study only, patients who are pregnant or lactating at trial entry or planning to become pregnant within 3 months after re-vaccination.

5 SCREENING AND CONSENT

5.1 Screening

Participants with an inadequate response to COVID-19 vaccination will be identified from participation in OCTAVE or other aligned SARS-CoV-2 vaccine studies (e.g. COVAD and PROSECO); or if SARS-CoV-2 anti-spike antibodies levels are available from disease site specific clinics; or for the solid cancer, haematopoietic stem cell transplant and CAR-T cell therapy disease cohorts only, a SARS-CoV-2 spike antibody response can be measured as a screening assessment using one of the assays listed in Appendix 1.

Those participants identified from pre-existing studies may receive a phone call or a letter of invitation (ethically approved template provided) from the Site Research Team.

Patients will be recruited at the clinical site by members of the clinical team who have been delegated this responsibility on the Site Signature and Delegation Log by the Principal Investigator.

An Eligibility Checklist should be completed prior to randomisation by the Investigator or designee. A copy should be returned to the Trial Office and the original filed in the Investigator Site File.

For the randomised sub-study only, women who are of child-bearing potential, a negative urine dipstick pregnancy test will be required prior to vaccination.

5.2 Informed Consent

It is the responsibility of the investigator or designee (e.g., registrars, Research Nurses if local practice allows and this responsibility has been delegated by the Principal Investigator) to obtain written informed consent for each participant before any trial related procedures. A Participant Information Sheet is provided to facilitate this process. Investigators must ensure that they adequately explain the aim of the trial and what the trial would involve for the participant.

The Joint Committee on Vaccination and Immunisation (JCVI) recommended on 01-Sep-2021 that a third primary dose be offered to individuals with severe immunosuppression in proximity to their first or second COVID-19 vaccine doses as part of their primary vaccination schedule (see <https://www.gov.uk/government/publications/third-primary-covid-19-vaccine-dose-for-people-who-are-immunosuppressed-jcvi-advice>). Invitations for this additional third primary vaccination were subsequently sent to patients who fall within this group. However, patients taking part in OCTAVE-DUO have already had this additional vaccine and should be advised at the point of consent not to take up this invitation.

The investigator should also stress that the patient is completely free to refuse to take part or withdraw from the trial at any time. The patient should be given ample time (ideally 24 hours) to read the Participant Information Sheet and to discuss their participation with others outside of the site research team. The patient must be given an opportunity to ask questions which should be answered to their satisfaction. The right of the patient to refuse to participate in the trial without giving a reason must be respected.

The informed consent process is expected to involve an interview between member(s) of the investigator team and the patient which should facilitate two-way communication. It is possible for this interview to be conducted remotely. Where this occurs, the patient can be sent the Participant Information Sheet in advance in the post or electronically. If the patient agrees to participate in the trial, they should be asked to sign and date the latest version of the Informed Consent Form. The Informed Consent Form should either be wet-ink signed by the patient and the investigator (or designee) or signed electronically using software which allows signature authentication (e.g., DocuSign). If wet-ink signed the Informed Consent Form can be returned when the patient attends for their first clinic appointment or it can be returned in the post, but it must be signed by both parties prior to the patient's entry into the trial.

Once the patient is entered into the trial, the participant's trial number should be entered on the Informed Consent Form. A copy of the Informed Consent Form should be given to the participant, a copy should be filed in the hospital notes, a copy sent to the Trial Office and the original placed in the Investigator Site File. Details of the informed consent discussions should be recorded in the patient's medical notes; including date of, and information regarding the initial discussion, the date consent was

given, with the name of the trial and the version numbers of the Participant Information Sheet and Informed Consent Form.

Throughout the trial the participant should have the opportunity to ask questions about the trial and any new information that may be relevant to the participant's continued participation should be shared with them in a timely manner. On occasion it may be necessary to re-consent the participant, in which case the process above should be followed and the participant's right to withdraw from the trial respected. Participants are permitted to re-consent at the same visit that new information is provided if they wish to do so. Details of these discussions (as specified above) should also be recorded in the patient's medical notes.

Electronic copies of the Participant Information Sheet and Informed Consent Form are available from the Trial Office and should be printed or photocopied onto the headed paper of the local institution.

Details of all patients approached about the trial should be recorded electronically on the Patient Screening/Enrolment Log.

The patient's General Practitioner (GP) should also be informed that they are taking part in the trial. A GP Letter template is provided electronically for this purpose.

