6 TRIAL ENTRY

After screening, the following will be checked prior to recruitment:

- Participant has provided consent and;
- Confirmation that the eligibility criteria have been met.

If eligibility is confirmed, the patient can be randomised into the trial.

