7.7 Participant Withdrawal

Participants may withdraw consent at any time during the trial. For the purposes of this trial two types of withdrawal are defined:

- The participant would like to withdraw from the trial but is willing to be followed up as standard (i.e., the patient has agreed that data can be collected at disease cohort specific clinic visits and used in the analyses); or
- The participant would like to withdraw from the trial entirely and is not willing to be followed up for the purposes of the trial (i.e., only data and blood samples collected prior to the withdrawal of consent can be used in the trial analysis) – withdrawal of consent.

The details of withdrawal (date, reason and type of withdrawal) should be clearly documented in the source data. A Withdrawal of Consent Form should be completed to notify the Trial Office of the participant's withdrawal from the trial.

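### Section 5.2 tells patients at consent to decline the national third primary dose for a reason that is not yet true, and no protocol step withdraws that advice from those who get no trial dose

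*Protocol*

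**What the plan says.** Section 5.2 reports that a third primary dose was recommended nationally for people with severe immunosuppression, and that invitations were then sent out. It goes on to say of those in the trial that they "have already had this additional vaccine and should be advised at the point of consent not to take up this invitation".

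The same section makes the investigator responsible "to obtain written informed consent for each participant before any trial related procedures". Section 6 then requires consent and confirmed eligibility before entry: "If eligibility is confirmed, the patient can be randomised into the trial". The Schedule of Events places re-vaccination after screening, trial entry and baseline.

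For the solid cancer, stem cell transplant and CAR-T cohorts, Section 5.1 adds that a "SARS-CoV-2 spike antibody response can be measured as a screening assessment using one of the assays listed in Appendix 1".

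On leaving the trial, Section 7.7 states: "Participants may withdraw consent at any time during the trial".

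**The concern.** The sentence in Section 5.2 is an operative instruction about clinical advice. It gives a reason (the dose has been given) and an action (decline the national offer), and it fixes the time of the action at consent. If the reason does not hold at that time, the investigator is asked to give a patient a false ground for refusing a recommended vaccine.

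This matters for people who consent, hear the advice, and then receive no trial dose. They belong to groups chosen because vaccination may work poorly in them. If nobody has to withdraw the advice, they may go without both the trial dose and the national one. The question is one of consent wording and patient safety. It does not touch sample size, power or type I error, and it is not something a statistical analysis plan would settle.

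**Working it through.** The protocol gives no figure on this point, so the check sets its sections side by side.

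**1. Doses received at the point of consent.**
- Inclusion criterion 2 (Section 4.1) asks for an inadequate response to two doses. A third dose is not a condition of entry.
- Section 12.2.1 defines the baseline measurement as the one before the third vaccination.
- Consent precedes every trial procedure (Section 5.2), eligibility and randomisation follow it (Section 6), and the re-boost is given at a later clinic attendance (Section 7.3.3).

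So at consent the count is two qualifying doses and no trial dose. The statement that the additional vaccine has already been given is untrue at that time.

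**2. Can another reading make it true?**
- *A third dose received outside the trial.* This contradicts the two-dose population in Sections 2.1.1, 3.1 and 4.1. Exclusion 1 tolerates a SARS-CoV-2 vaccine 14 or more days before entry, but does not require a third one.
- *Participants already vaccinated in the trial when their invitation arrived.* The reason would be true for them, but they are past the point of consent, which is when the sentence places the advice.
- *The trial dose will count as the third primary dose.* This is sensible and almost certainly meant, but it is not what is written.

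**3. Who can be advised and then not vaccinated?**
- *Failed antibody screen.* Sections 5.1 and 7.3.1 and the Schedule of Events allow in-trial screening in three cohorts; Section 8.2 names only stem cell transplant and CAR-T. Because consent precedes trial procedures, this result comes after the advice. The national recommendation, as Section 5.2 reports it, rests on severe immunosuppression and mentions no antibody level, so failing the screen does not by itself remove someone from it.
- *Withdrawal before vaccination.* Section 7.7 permits withdrawal at any time. There can be a gap in which this happens: the baseline sample may be taken up to 14 days before the dose (Section 7.3.2), and Pfizer or Moderna vaccination is postponed for acute severe febrile illness with no stated limit (Section 7.2).
- Lack of Novavax supply is not such a route, because Section 3.1 re-randomises those patients to Pfizer or Moderna.

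**4. Does any step withdraw the advice?**
- Section 5.2 requires that new information relevant to the participant's "continued participation should be shared with them in a timely manner". That does not fit someone who has left or never entered.
- Section 5.2 also says that the patient's "General Practitioner (GP) should also be informed that they are taking part in the trial". Nothing is to be sent if the patient is then not vaccinated.
- Section 7.7 asks for the details to be recorded and says: "A Withdrawal of Consent Form should be completed to notify the Trial Office". It does not mention vaccination.
- The three-month follow-up (Section 7.3.5), adverse event reporting (Section 8) and the list of forms (Section 9) contain no such step either.

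**The case against.** The strongest reply has four parts.

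First, the instruction concerns patients taking part. A screen failure never takes part and a full withdrawal stops doing so, so the ground for declining the national dose lapses by itself. This is a fair reading of the intent. It does not cure the text, because the advice is given at consent, when nobody knows who will pass the screen or stay, and the person who heard it has no reason to think it has lapsed.

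Second, a line telling leavers to take up the national dose may well stand in the Participant Information Sheet or the GP letter template, and neither is shown. This stands. The point is limited to what the protocol itself instructs, and it is more certain about the wrong reason than about any harm.

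Third, exposure is narrow. Recruitment is by clinical teams, who may correct the advice unprompted. Some who withdraw agree to continued follow-up at their clinics. On the quantitative assays, a failed screen means an antibody level above the low-response range. The protocol also does not say which cohorts fall within the severe immunosuppression group. All of this stands, and it keeps the severity low.

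Fourth, a reader might infer that the advice should be held back until eligibility is confirmed. The documents do not support that. Forgoing the national dose is part of what a patient agrees to and should be known when deciding. A national dose taken in the interval would conflict with the two-dose population, or fall inside the 14-day limit in exclusion 1.

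**Conclusion.** The point holds as a minor correction. The reason given in Section 5.2 is false at the time it is to be used, and the protocol contains no step that withdraws the resulting advice from people who then receive no trial dose. The first part follows directly from the protocol's own sequence. The second is a statement about the protocol alone and assumes nothing about the unseen patient and GP documents.

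Two stronger conclusions might be drawn, and neither is supported. A reader might try to size the problem from the allowance of 60 participants for withdrawal or loss in Section 12.2.6.1. That allowance covers loss at any time, does not separate out loss before vaccination, and leaves out screen failures; the number affected is unknown. A reader might also suspect bias in the primary result. The primary comparison is paired and uses a baseline sample taken after consent and before the re-boost, and nothing in this wording disturbs it.

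**What to change.** 1. In Section 5.2, keep the advice at consent but reword it along these lines: *the trial re-boost will serve as the third primary dose, so participants should not also take up the national invitation, provided that they receive the trial dose.*
2. Add one sentence to Section 5.2 and one to Section 7.7: anyone not vaccinated in the trial, whether through a failed screen, withdrawal before vaccination or another reason, is promptly told to take up the national invitation, and so is their GP.
3. Check that the Participant Information Sheet and the GP letter say the same, and add a matching line where they do not.

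The cost is one reworded passage, two added sentences and a line to the GP, handled as a protocol amendment. Eligibility, randomisation, sample size and analysis are unchanged.
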